5.2 Exclusion Criteria

Subjects who meet any of the following criteria will not qualify for the study.

1. Any concomitant disease or disorder that has symptoms of spasticity or that may influence the subject's level of spasticity.
2. Inability to rate their level of spasticity or distinguish it from other MS symptoms.
3. Acute MS exacerbation/relapse requiring treatment or disease modifying drug dose alteration within 3 months of Visit 1 (Screening).
4. Use of high dose (120 mg daily) oral or intravenous methylprednisolone, or equivalent, within 3 months before Visit 1 (Screening).
5. Concomitant use of medications that would potentially interfere with the actions of the study medication or outcome variables (Appendix 6).
6. Use of botulinum toxin A or B for spasticity within 6 months of Visit 1 (Screening).

² GFR Calculator:

$GFR (mL/min/1.73 m^2) = 175 \times (Scr (mg/dL))^{-1.154} \times (Age (years))^{-0.203} \times (0.742 \text{ if female}) \times (1.212 \text{ if African American})$ (conventional units)

$GFR (mL/min/1.73 m^2) = 175 \times (Scr (\mu mol/L)/88.4)^{-1.154} \times (Age (years))^{-0.203} \times (0.742 \text{ if female}) \times (1.212 \text{ if African American})$ (SI units)

7. Pregnancy, lactation, or planned pregnancy during the course of the study and for 3 months after the final study visit.
8. Recent history (within past 12 months) of any unstable psychiatric disease (or any yes response to questions 1 or 2 on the Columbia–Suicide Severity Rating Scale [C-SSRS] at Screening), or current signs and symptoms of significant medical disorders such as severe, progressive, or uncontrolled pulmonary, cardiac, [REDACTED] hepatic, renal, genitourinary, hematological, endocrine, immunologic, or neurological disease.
9. History of epilepsy.
10. Current significant cognitive deficit, severe or untreated anxiety, severe or untreated depression.
11. Subjects with abnormal micturition that requires indwelling or intermittent catheterization or with lower urinary tract symptoms (LUTS) that result in a score >26 in the Visit 2 (Baseline) Urinary Symptom Profile – USP[®] (USP) questionnaire (Appendix 7). Subjects who are proficient in self-catheterization may be included in the study at investigator discretion.
12. Subject has clinically significant abnormal laboratory values, in the opinion of the investigator, at Visit 1 (Screening).
13. Current malignancy or history of malignancy that has not been in remission for more than 5 years, except effectively treated basal cell skin carcinoma.
14. Any other significant disease, disorder, or significant laboratory finding which, in the opinion of the investigator, puts the subject at risk because of participation, influences the result of the study, or affects the subject’s ability to participate.
15. Planned elective surgery or other procedures requiring general anesthesia during the course of the study.
16. History of any illicit substance abuse (eg, alcohol, cocaine) or prescription for long-acting opioids within the past 12 months (tramadol use will be allowed).
17. Participation in another clinical research study within 1 month of Visit 1 (Screening).

6 STUDY PROCEDURES

Table 1 and the following subsections present the planned study visits, timing, and details for study procedures. Figure 1 presents the timeline diagram for the study.

As footnoted in Table 1, the TNmAS-MAL assessment will always be performed by the study evaluator (someone other than the investigator) who has been appropriately trained to perform and assess the TNmAS-MAL, and when possible all TNmAS-MAL assessments should be performed for a particular subject by the same study evaluator throughout the study. The TNmAS-MAL assessment should be conducted prior to any scheduled study procedures. The most affected limb will be determined by the study evaluator. The study evaluator must remain blinded to the subject's overall clinical, safety, and CGIC assessments. The investigator or sub-investigator will perform the other assessments (EDSS, C-SSRS) and has access to the findings of the TNmAS-MAL when conducting the CGIC.

Table 1: Schedule of Assessments, Study OS440-3004

Procedure	Screening Visit 1 Days -21 to 0	Baseline Visit 2 Day 1 (±3 days)	Visit 3 Day 10 (±3 days)	Visit 4 Day 42 (±5 days)	Visit 5 Day 84 (±5 days)	Final or Early Termination Visit 6 Day 92 (±5 days)
Written informed consent	X					
Inclusion and exclusion criteria	X	X				
Review study discontinuation criteria		X	X	X	X	
Withdrawal anti-spasticity medication	X					
Assign enrollment number	X					
Randomization		X				
Demography	X					
Medical/surgical history	X					
Physical examination	X					
Height	X					
Weight	X					X
Vital signs ¹	X	X	X	X	X	X
Hematology/serum chemistry/urinalysis	X	X	X	X	X	X
Electrocardiogram	X					X
Pregnancy test ²	X	X	X	X	X	X
Dispense study medication		X	X	X	X	
Collect unused study medication			X	X	X	X
C-SSRS	X	X	X	X	X	X
TNmAS-MAL ³	X	X		X	X	X
EDSS ⁴	X	X				X
CGIC ⁴				X	X	X
PGIC						X
USP [®] questionnaire	X	X	X	X	X	X
Adverse event assessment		X	X	X	X	X
Concomitant medications/therapies	X	X	X	X	X	X

[figure not shown]
C-SSRS = Columbia–Suicide Severity Rating Scale; TNmAS-MAL = Total Numeric-transformed modified Ashworth Scale score of the most affected limb; EDSS = Expanded Disability Status Scale; CGIC = Clinical Global Impression of Change; PGIC = Patient Global Impression of Change; USP = Urinary Symptom Profile.

(footnotes on next page)

Table 1 - Footnotes:

1. Vital signs will be measured with the subject in a supine position and 3 minutes subsequently in a standing position after the supine assessment is completed. Body temperature and respiratory rate will be measured only during the supine assessment.
2. Premenopausal women of childbearing potential must have a negative serum pregnancy test within 21 days before Visit 2 (Baseline). Urine pregnancy testing will be performed at Visits 2 through 6.
3. The TNmAS-MAL assessment will be performed prior any scheduled lab draws and will always be done by the study evaluator (someone other than the investigator) who has been appropriately trained to perform and assess the TNmAS-MAL, and when possible all TNmAS-MAL assessments should be performed for a particular subject by the same study evaluator throughout the study. The most affected limb will be determined by the study evaluator.
4. Performed by the investigator or sub-investigator not functioning as the study evaluator for the particular subject.

Figure 1: Timeline Diagram, Study OS440-3004

6.1 Visit 1 (Screening) – Days –21 to 0

Each potential study subject will have a Screening visit (Visit 1) within 21 days prior to randomization at the Baseline visit (Visit 2). At Screening, the investigator will fully explain to the subject the objectives, characteristics, and procedures for the study. Rescreening of subjects will only be allowed for delays in screening (eg, >21 days) that have occurred due to technical errors (eg, issue with the Interactive Response Technology [IRT] system, or with delivery or assessment of laboratory tests, etc). Screening assessments/procedures will include the following:

- Obtain a signed and dated ICF from each subject prior to any study-specific procedures being conducted ([Section 13.3](#)).
- Assess eligibility according to the inclusion ([Section 5.1](#)) and exclusion criteria ([Section 5.2](#)).
- After establishing the subject's eligibility to participate, explain to the subject how to withdraw all anti-spasticity medication (up to a 21-day period) prior to the next visit ([Section 7.7](#)).
- Assignment of an enrollment number ([Section 7.4](#)).
- Record demographic data, including age, sex, race, and ethnicity.
- Record medical and surgical history ([Section 9.1](#)).
- Record physical examination results ([Section 9.3](#)).
- Record weight and height ([Section 9.4](#)).
- The study evaluator will perform the TNmAS-MAL ([Section 8.1](#)).
- Record vital sign measurements, including blood pressure (BP), heart rate, respiratory rate, and body temperature ([Section 9.2](#)).
- Collect blood and urine samples for hematology, serum chemistry, and urinalysis ([Section 9.5](#)). Subject should be fasting if possible. As per Exclusion Criterion 12, if, in the opinion of the investigator, a subject has clinically significant abnormal laboratory value(s) at Visit 1 (Screening), they will be excluded from the study.
- Perform a standard 12-lead electrocardiogram (ECG) ([Section 9.6.1](#)).
- Collect a blood sample for serum pregnancy testing for women of childbearing potential. Because contraception is required throughout the study for both males and females, the use of an acceptable method throughout the study will be discussed with all subjects ([Section 7.8](#)).
- Administer the C-SSRS ([Section 9.6.3](#)).

- Administer the EDSS ([Section 8.4](#)).
- Administer the USP questionnaire ([Section 9.6.2](#)).
- Record all concomitant medications/therapies the subject is currently taking ([Section 7.7](#)).
- Schedule the next visit within approximately 7 to 14 days.

6.2 Visit 2 (Baseline) – Day 1 (±3 days)

This visit takes place after the subject has completed withdrawal of all anti-spasticity medications. Assessments/procedures will include the following:

- Review eligibility according to the inclusion ([Section 5.1](#)) and exclusion criteria ([Section 5.2](#)).
- Review study discontinuation criteria ([Section 12.4](#)).
- Verify complete washout and abstinence from oral anti-spasticity medications for at least the past 14 days ([Section 7.7](#)).
- If the subject is eligible for randomization, obtain a randomization code and medication kit number for that subject ([Section 7.4](#)).
- The study evaluator will perform the TNmAS-MAL ([Section 8.1](#)).
- Record vital sign measurements, including BP, heart rate, respiratory rate, and body temperature ([Section 9.2](#)).
- Collect blood and urine samples for hematology, serum chemistry, and urinalysis ([Section 9.5](#)). Subject should be fasting if possible. As per Exclusion Criterion 12, if, in the opinion of the investigator, a subject has clinically significant abnormal laboratory value(s) at Visit 2 (Baseline), they will be excluded from the study.
- Collect a urine sample for pregnancy testing for women of childbearing potential ([Section 7.8](#)).
- Dispense the study medication. The Investigator will explain to the subject how to take the study medication and the regimen to be followed until the next visit ([Section 7.5](#)).
- The site will administer the first daily dose of study medication to the subject.
- Administer the C-SSRS ([Section 9.6.3](#)).
- Administer the EDSS ([Section 8.4](#)).
- Administer the USP questionnaire ([Section 9.6.2](#)).
- Record any adverse events (AEs) that have occurred ([Section 9.7](#)).

- Record all concomitant medications/therapies the subject is currently taking ([Section 7.7](#)).
- Schedule the next study visit.

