7.4 Method of Assignment of Study Drug

Two doses of AERT, 40 mg (20 mg BID) and 80 mg (40 mg BID), will be compared with placebo. The treatment groups will be randomized in a 1:1:1 ratio.

After Screening procedures have been completed, authorized site personnel will acknowledge that the applicable subject met all the specified inclusion criteria ([Section 5.1](#)) and none of the exclusion criteria ([Section 5.2](#)) and an enrollment number will be sequentially assigned. After the Screening clinical laboratory test results and other clinical assessments have been completed at Visit 2 (Baseline), assignment to a treatment group will then follow a predetermined list of randomization numbers, with each successive number receiving 1 of the 3 treatments in random order. Authorized site personnel will use the IRT system to assign a kit number that corresponds to the randomization schedule. The kit box with the assigned kit number will be dispensed to the subject.

The randomization code will be provided by the CRO.

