9.5 Clinical Laboratory Tests

A central laboratory will be used for this study. Blood draws for chemistry and hematology tests and urine samples for urinalyses will be collected and sent to the central laboratory. Table 4 presents the specific clinical laboratory tests to be evaluated.

All laboratory values that are outside of the normal range for that parameter will be so flagged when reported to the site. The investigator will annotate laboratory reports to indicate whether any abnormal laboratory value is considered clinically significant. Any abnormal laboratory value that is considered clinically relevant should be confirmed by a repeated laboratory test when possible. If a clinically significant laboratory abnormality requires treatment or is the reason for a subject being discontinued from the study, the abnormal result must be classified as an AE. If clinically relevant and considered an AE, the event must be followed until resolution or as long as medically necessary and be recorded on the AE page of the eCRF/CRF.

Table 4: Clinical Laboratory Tests, Study OS440-3004

Hematology	Urinalysis	Serum Chemistry
Hematocrit	Bilirubin	Alanine aminotransferase (ALT)
Hemoglobin	Blood	Albumin
Platelet count	Glucose	Alkaline phosphatase
Red blood cell (RBC) count	Ketones	Aspartic acid transaminase (AST)
White blood cell (WBC) count with differential	Leukocytes esterase	Bicarbonate
	Specific gravity	Blood urea nitrogen (BUN)
	Color	Chloride
	pH	Creatinine
	Protein	Creatinine kinase
	Microscopic examination of urine:	Glucose
	• Epithelial cells	Potassium
	• Casts (RBC, WBC, etc.)	Sodium
	• Red blood cells	Total bilirubin (if elevated, obtain direct bilirubin)
	• White blood cells	Uric acid
	Urine pregnancy test (at the site)	

Samples for clinical hematology, serum chemistry, and urinalysis will be obtained for each subject and sent to a central laboratory at the visits specified in Table 1. Site personnel will do a routine urinalysis by dipstick on site and the central laboratory will do a complete microscopic urine examination. Site personnel will also complete a urine pregnancy test for female subjects of childbearing potential on site at the visits specified in Table 1 (see [Section 7.8](#) regarding serum pregnancy testing in premenopausal women of childbearing potential at Screening).

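### Protocol Section 6.2 applies Exclusion 12 to Visit 2 laboratory values, which that criterion does not cover and which would probably be known only after randomisation and first dose

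*Protocol*

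**What the plan says.** **Eligibility.** Exclusion 12 in Protocol Section 5.2 reads "Subject has clinically significant abnormal laboratory values, in the opinion of the investigator, at Visit 1 (Screening". The Visit 1 procedures in Section 6.1 cite the same criterion consistently: "clinically significant abnormal laboratory value(s) at Visit 1 (Screening), they will be excluded from the study". The Visit 2 procedures in Section 6.2 also cite Exclusion 12, but for the later sample: "clinically significant abnormal laboratory value(s) at Visit 2 (Baseline), they will be excluded from the study". Exclusion 14 separately allows exclusion for a significant laboratory finding that, in the investigator's opinion, puts the subject at risk. It names no visit, and Section 6.2 does not cite it.

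**Timing.** Section 6.2 has the site do the following at Visit 2: "If the subject is eligible for randomization, obtain a randomization code and medication kit number for that subject". At the same visit, "The site will administer the first daily dose of study medication to the subject". Section 7.4 sets the condition for assignment: "After the Screening clinical laboratory test results and other clinical assessments have been completed at Visit 2 (Baseline), assignment to a treatment group" then follows the randomisation list. Section 9.5 states "A central laboratory will be used for this study". Only the urine dipstick and urine pregnancy test are read on site.

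**Subjects who leave.** Section 12.4 counts anyone who withdraws after randomisation and before completing Visit 6 as prematurely discontinued, and withdrawn subjects are not replaced. Section 6.5 asks for the Visit 6 assessments in all subjects, including those who leave early. ITT is all randomised subjects (Protocol 11.2, SAP 7.1.2). The Safety population needs one dose and one post-dose visit (Protocol 11.2, SAP 7.1.5).

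**The concern.** Section 6.2 relies on a criterion that does not cover the sample it refers to. That would be a cross-reference slip if the results were available before assignment. Here the sample is drawn at the visit where the subject is randomised and dosed. A rule worded as an eligibility check would then probably operate as a withdrawal rule.

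Neither document says how such a subject is to be classed. Section 6.2 speaks of exclusion, and Section 12.4 would call the same event premature discontinuation. The answer affects the disposition table, the imputation rule in one sensitivity analysis, the visit to which termination scores are assigned, and membership of the Safety population. Subjects whom Section 6.2 treats as ineligible may also already have received study drug.

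**Working it through.** The check is mainly textual. The only figure to reproduce is the planned size: 3 × 170 = 510, which agrees with Protocol Section 5.

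**1. Does the cited criterion cover Visit 2?** No. Exclusion 12 and Section 6.1 both name Visit 1, and Section 6.2 names Visit 2.

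**2. Are Visit 2 results needed before assignment?** Section 7.4 names the Screening laboratory results and other clinical assessments. It does not name Visit 2 laboratory results. Chemistry and haematology samples are sent away, and the first dose is given at the same visit. Late arrival is therefore the likely sequence, though it is inferred. The order of the list in Section 6.2 is not evidence either way: TNmAS-MAL is listed after the randomisation step, yet Section 6 requires it before other procedures.

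**3. What happens to the efficacy data?** Take a subject who leaves on Day 5 (an illustrative day, within the 9-day titration).
- Distance to Visit 2 (Day 1) is 5 − 1 = 4 days; distance to Visit 3 (Day 10) is 10 − 5 = 5 days. Visit 2 is closest.
- SAP 7.3.3 assigns termination data to the closest scheduled visit or, if that visit has valid data, to the next available one. Visit 2 already holds the baseline TNmAS-MAL.
- Visit 3 collects no TNmAS-MAL. If the next available visit means the next one at which the measure is scheduled, the score is analysed as Day 42, which is 42 − 5 = 37 days after it was taken. If it means Visit 3, the score does not enter the MMRM, which uses Days 42 and 84 only.
- If no termination assessment is done, the subject has no post-baseline score.

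The data are thus either mistimed or missing from the primary model.

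**4. What happens in the mWOCF analysis?** Section 9.5 requires a clinically significant laboratory abnormality that is the reason for discontinuation to be classified as an AE. SAP 7.3.2.2 uses WOCF for withdrawals due to an AE and LOCF for all others. A pre-dose abnormality could therefore move the subject from LOCF to WOCF. With a single post-baseline score the two rules give the same value unless the baseline score counts as an observation, which the SAP does not say.

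**5. How large is the effect?** The rate of Visit 2 laboratory exclusions is not given; 1% to 10% is assumed. The effect size, SD and power behind the sample size are not visible in the available copies, so design power is assumed to be 80% or 90% for one comparison at 170 per arm, two-sided 0.05. Flagged subjects are treated as fully lost, with equal rates across arms.

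Detectable standardised difference: d = √(2/170) × (1.96 + z_power), which is 0.3039 at 80% and 0.3516 at 90%. Reduced power: Φ(d × √(n/2) − 1.96), with n = 170 × (1 − rate).

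| Assumed rate | Subjects of 510 | n per arm | Power if 80% planned | Power if 90% planned |
|---|---|---|---|---|
| 1% | 5.1 | 168.3 | 79.6% | 89.7% |
| 2% | 10.2 | 166.6 | 79.2% | 89.4% |
| 5% | 25.5 | 161.5 | 78.0% | 88.5% |
| 10% | 51.0 | 153.0 | 75.7% | 86.8% |

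**The case against.** The best defence is that this is a faulty cross-reference with little consequence. Several parts of it stand.

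- **Timing is not stated.** No laboratory turnaround appears anywhere, and the on-site dipstick can be read before dosing. A reader might infer that all Visit 2 results necessarily arrive after dosing. The documents support only that the blood results probably do.
- **Exclusion 14 gives some basis.** It names no visit, and Section 6.2 has all criteria reviewed again at Visit 2. A Visit 2 laboratory exclusion is therefore not without authority. But Section 6.2 cites a different criterion, and Exclusion 14 does not resolve the timing.
- **ITT is protected.** A reader might infer that these subjects are removed from the primary analysis set. They are not: ITT is all randomised subjects, analysed as randomised. The exclusion is from the study.
- **Data are not necessarily absent.** A reader might infer that these subjects have no Day 42 or Day 84 record. Section 6.5 asks for TNmAS-MAL and CGIC at termination, and SAP 7.3.3 may assign those scores to a later visit. The risk is mistimed data as well as missing data.
- **Safety membership is usually kept.** An attended termination visit after dosing is a post-dose visit. Only a subject who misses it drops out, and that is a general feature of the definition.
- **The numbers are probably small.** Subjects have already passed a laboratory check at Screening, and pre-dose samples should flag similar proportions in each arm.

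What remains is that following the text as written would probably withdraw randomised, dosed subjects, with their classification left open.

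**Conclusion.** The inconsistency is real and affects conduct. Section 6.2 conflicts with Exclusion 12 and Section 6.1, and it fits poorly with the assignment condition in Section 7.4. Its probable effect is early withdrawal of exposed subjects, who stay in ITT with missing or mistimed efficacy scores, possible treatment as AE withdrawals in the mWOCF analysis, and loss from Safety if no post-dose visit occurs.

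The frequency is unknown. On the assumptions above, a rate of 1% to 2% costs less than one percentage point of power; at 10% the cost is about 3 points from 90% and about 4 from 80%. No material bias between arms is expected, because the samples precede dosing. The point rests on contradictory eligibility text and undefined handling, and on the inference that central results come back after the visit. It should be corrected, but it does not threaten the primary conclusion.

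**What to change.** **Protocol.** Reconcile Exclusions 12 and 14 with Sections 6.1, 6.2, 7.4 and 9.5, so that the laboratory eligibility rule and the timing of randomisation agree. Which rule applies, and the clinical handling of an abnormal Visit 2 result, are for the sponsor to decide.

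**SAP.** Add, before unblinding, that:
- a subject randomised before an abnormal Visit 2 result is known is, if withdrawn, classed as a post-randomisation discontinuation;
- an abnormality in a pre-dose sample does not count as an AE withdrawal for mWOCF;
- termination scores from the first days after dosing are not analysed as Day 42 (SAP 7.3.3);
- a dosed subject is not dropped from Safety for lack of a post-dose visit. This changes the definition in Protocol 11.2 and SAP 7.1.5, so both need the edit.

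The cost is wording in the protocol and a few sentences in SAP 7.1 and 7.3. No new data collection or change in sample size is needed.

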6.3 Visit 3 – Day 10 (± 3 days)

Assessments/procedures will include the following:

- Review study discontinuation criteria ([Section 12.4](#)).
- Record vital sign measurements, including BP, heart rate, respiratory rate, and body temperature ([Section 9.2](#)).
- Collect blood and urine samples for hematology, serum chemistry, and urinalysis ([Section 9.5](#)).
- Collect a urine sample for pregnancy testing for women of childbearing potential ([Section 7.8](#)).
- Dispense the study medication. The Investigator will explain to the subject how to take the study medication and the regimen to be followed until the next visit ([Section 7.5](#)).
- Collect unused study medication, assess compliance, and study drug accountability ([Section 7.9](#)).
- Administer the C-SSRS ([Section 9.6.3](#)).
- Administer the USP questionnaire ([Section 9.6.2](#)).
- Record any AEs that have occurred ([Section 9.7](#)).
- Record all concomitant medications/therapies the subject is currently taking ([Section 7.7](#)).
- Schedule the next study visit.

6.4 Visit 4 – Day 42 (± 5 days) and Visit 5 – Day 84 (± 5 days)

Assessments/procedures for both visits will include the following:

- Review study discontinuation criteria ([Section 12.4](#)).
- The study evaluator will perform the TNmAS-MAL ([Section 8.1](#)).
- Record vital sign measurements, including BP, heart rate, respiratory rate, and body temperature ([Section 9.2](#)).
- Collect blood and urine samples for hematology, serum chemistry, and urinalysis ([Section 9.5](#)).

- Collect a urine sample for pregnancy testing for women of childbearing potential (Section 7.8).
- Dispense the study medication. The Investigator will explain to the subject how to take the study medication and the regimen to be followed until the next visit (Section 7.5).
- Collect unused study medication, assess compliance, and study drug accountability (Section 7.9).
- Administer the C-SSRS (Section 9.6.3).
- Administer the USP questionnaire (Section 9.6.2).
- Record any AEs that have occurred (Section 9.7).
- Determination of the CGIC by the Investigator (Section 8.2).
- Record all concomitant medications/therapies the subject is currently taking (Section 7.7).
- Schedule the next study visit.

